#### 4.3 Sample size calculation

Based on WHO definitions, mass screening includes every person in a vulnerable community. The combined prisons of Tacumbú, Esperanza, Buen Pastor house around 4700 PPL. An additional 500 employees (estimated number, to be confirmed) who are in direct contact with the PPL will also be included. Based on calculations we expect to detect around 200-240 cases of active tuberculosis in prisoners (3-6% of 4000 PPL) and 0-5 cases in employees (estimated 0.2% of 1000 employees). The number of expected cases in the latter group could be an underestimation as these people are in constant contact with PPL and have a higher risk than the general population of active TB.

The study sample size is based on the need for at least 100 cases with active TB to build a robust AeoNose™ neural network (calibration model) and subsequently another 100-150 cases to make a blind prediction (validation model). A systematic literature review of acceptability of TB screening among risk groups showed an average percentage of screening consent of 72% among prisoners. (range 18-100%, Mitchell et al. 2012)

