## 3. STUDY DESIGN

Diagnostic prospective cohort study: mass screening through conventional symptoms screening by a doctor, a physical exam and with testing of CAD4TB® and AeoNose™ as well as bacteriological testing of presumptive cases.

An estimated 5000 individuals will be invited to participate. All prisoners and employees will be eligible for inclusion. The sample size is based on an estimated incidence of 3000-5000/100.000 and a presumptive number of 150-250 active TB cases to be found in order to have enough cases to first train the neural network (with at least 500 - 1000 healthy individuals and a 100 active TB cases) and then perform the blind predictions on the rest of the participants to establish sensitivity and specificity of the AeoNose™.

The study consists of one primary visit and, in case of suspicion of presumptive TB but no confirmed TB or alternative diagnosis, two follow-up visits after three and six months respectively. The estimated total study duration will be from February 2020 to May 2021. The study settingwill be the Buen Pastor, Esperanza and Tacumbú prisons in Asunción, Paraguay Required condition to perform the study in each of these three institutions is safety for the study team and also the guards and prisoners. In case of unstable conditions we will look for an alternative penal institution.

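### Section 4.3's 200-240 expected prisoner TB cases do not follow from 3-6% of 4000 (which is 120-240), so the 200-250 cases needed to calibrate and validate the AeoNose are not assured

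*Protocol*

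**What the plan says.** Section 4.3 gives the expected yield among prisoners: "Based on calculations we expect to detect around 200-240 cases of active tuberculosis in prisoners (3-6% of 4000 PPL"). It adds "0-5 cases in employees (estimated 0.2% of 1000 employees"). Just before this, it gives other population figures: "The combined prisons of Tacumbú, Esperanza, Buen Pastor house around 4700 PPL" and "An additional 500 employees (estimated number, to be confirmed").

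The purpose of the count follows in the same section: "The study sample size is based on the need for at least 100 cases with active TB" to build the AeoNose calibration model, "and subsequently another 100-150 cases to make a blind prediction (validation model"). The section closes with a literature review that "showed an average percentage of screening consent of 72% among prisoners" (range 18-100%).

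Section 3 has its own version: "An estimated 5000 individuals will be invited to participate", with a rate of 3000-5000 per 100,000 (3-5%) and 150-250 active cases. About 100 of these train the network and the remaining participants are used for blind prediction. The Summary and section 1 also give 3-5%. Section 8.1 describes the split as a proportion, aiming for at least 30-40% of all TB cases in the calibration set.

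**The concern.** The lower bound of 200 does not follow from the rate and denominator printed beside it. Either the count or the rate is wrong, and the text does not say which. The slip falls on the figure that matters most: 200 is exactly the sum of the two minimum requirements (100 + 100). A reader of section 4.3 would conclude that the minimum is met across the whole expected range, when the section's own 3% falls well short of it.

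The conflicting inputs make the intended figure hard to recover. The 4000 may be an allowance for refusals among 4700 (4000/4700 = 85%), but the text does not say so, and it does not match the 72% cited in the same section.

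At stake is the precision of AeoNose sensitivity, which belongs to the first primary objective, or else the size of the calibration set. CAD4TB needs no calibration split here.

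**Working it through.** **Inputs.** Section 4.3: 4700 and 4000 prisoners; 500 and 1000 employees; 3-6% in prisoners; 0.2% in employees; 72% consent; a need of at least 100 plus 100-150 cases. Section 3: 5000 invited; 3-5%; 150-250 cases. Section 8.1: calibration share of at least 30-40%. Section 5.2: 88% sensitivity in the earlier Asunción pilot, used below only as an illustration.

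**The plan's own figures** (cases = number of people × rate):
- 0.03 × 4000 = 120 and 0.06 × 4000 = 240. The upper end reproduces; the lower end of 200 does not.
- 200/4000 = 5.0% and 240/4000 = 6.0%, so 200-240 corresponds to 5-6%.
- With the other base, 0.03 × 4700 = 141 and 0.06 × 4700 = 282. This does not give 200-240 either.
- Section 3: 0.03 × 5000 = 150 and 0.05 × 5000 = 250. This reproduces, but it applies the prison rate to employees as well.
- Section 3's rates with section 4.3's 0.2% for employees: 4000 prisoners and 1000 employees give 120 + 2 = 122 to 200 + 2 = 202; 4700 and 500 give 141 + 1 = 142 to 235 + 1 = 236.

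**Prisoner cases by base and rate, and the rate needed for 200 or 250 cases.** At 72% consent, 4700 × 0.72 = 3384.

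| Prisoners screened | 3% | 5% | 6% | Rate for 200 | Rate for 250 |
|---|---|---|---|---|---|
| 4000 | 120 | 200 | 240 | 5.0% | 6.25% |
| 4700 (no refusals) | 141 | 235 | 282 | 4.3% | 5.3% |
| 3384 (4700 at 72%) | 102 | 169 | 203 | 5.9% | 7.4% |

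With 4000 prisoners, 250 is not reached even at 6%. At 0.2%, 500 or 1000 employees means 1 or 2 cases, so that mismatch is numerically trivial.

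**What a low yield does to the split.**
- Keeping section 4.3's 100 calibration cases: 120 − 100 = 20 left for validation; section 3's 150 − 100 = 50.
- Using 30-40% as in section 8.1: a total of 120 gives 36-48 calibration and 72-84 validation cases; a total of 150 gives 45-60 and 90-105.

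**Illustrative precision.** Wilson 95% intervals at an assumed sensitivity of 88%:

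| Validation cases | Interval |
|---|---|
| 20 | 67-96% |
| 50 | 76-94% |
| 72 | 79-94% |
| 84 | 79-93% |
| 100 | 80-93% |

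**The case against.** The arithmetic slip is plain; the case against concerns its consequences.

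- **The split is proportional in section 8.1.** With 30-40% for calibration, 120 cases still leave 72-84 for validation, and the interval is little wider than with 100. This stands as far as validation precision goes: the 20-case figure holds only if the fixed 100 is kept. It does not rescue the target, because 36-48 calibration cases are far below the stated minimum of 100. One of the two requirements fails either way.
- **Section 3 already discloses a lower yield.** Its 150-250, with about 100 for training, implies as few as 50 for validation. This is true, and the two case ranges overlap. It shows that the shortfall can be worked out elsewhere in the protocol; it does not correct section 4.3.
- **Some mismatches are mild.** 4000 + 1000 equals section 3's 5000. The 500 is marked as provisional and limited to staff in direct contact with prisoners, so it may be a subset of the 1000. With 4700 and 500, section 3's rates give 142-236, close to its 150-250. These points stand, but the text does not explain any of them.
- **Cases could be added.** People with known or treated TB are eligible (section 4.2), and follow-up, passive detection and empirically treated responders may add more. No numbers are given, and nothing in section 4.3 attributes the 200 to them.
- **Nothing stated depends on 200.** The protocol gives no power or precision target, and everyone in the three prisons is invited. This limits the severity.

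**Conclusion.** The concern holds; it should be fixed but does not threaten the design. Section 4.3's lower bound is wrong as written: 3% of 4000 is 120, which is 80 cases (40%) below the stated 200. The stated need of 200-250 cases is therefore not assured. On the protocol's own inputs, the minimum of 200 is met only from a prisoner rate of 5.0% (4000 prisoners), 4.3% (4700, no refusals) or 5.9% (4700 at 72% consent).

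The target is not out of reach: with 4700 prisoners and full participation, the required 4.3% lies inside section 3's 3-5%. The 20- and 50-case validation sets are conditional on keeping 100 cases for calibration. The intervals assume 88% sensitivity, and the 72% scenario applies the cited average to all 4700. Cases from known or treated TB and from follow-up are not counted because the protocol gives no figure for them.

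**What to change.** Restate sections 3 and 4.3 from one set of inputs:

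- one prisoner base, one employee number, one prisoner rate range and a separate employee rate, used in both sections;
- an explicit consent assumption with a range, for example 72% and 100%. If 4000 is meant as an allowance for refusals among 4700, say so;
- a corrected lower bound (120 if 3% of 4000 is kept) or a corrected rate (5-6% if 200-240 is kept and can be supported);
- the resulting calibration and validation case numbers at the low and high ends, stating which split applies when cases are few: section 4.3's minimum of 100 or section 8.1's 30-40%;
- a statement of the prisoner rate from which 100 + 100 is met under the chosen base and consent.

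The cost is text and figures in two sections, with no extra enrolment and no design change. The drawback is that the stated case numbers will look less favourable.

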#### 5. INVESTIGATIONAL PRODUCT

#### 5.1 Name and description of investigational product(s)

- AeoNose™ (the eNose Company, Zutphen, the Netherlands):
- The Aeonose™ is a diagnostic device for exhaled-breath analysis. It is portable and requires a participant to breathe through the device for five minutes at tidal breathing.
  Volatile organic compounds (VOC) in the breath are captured by metal-oxide sensors. The unique 'smell print' of TB can be identified by an algorithm that is built on a de-blinded sample of the population in the calibration phase using an artificial neural network.
- CAD4TB® (Delft Imaging, Veenendaal, the Netherlands):

The CAD4TB® software analyses an X-ray image and detects the many different abnormal structures that may be related to TB. The system has been trained in the detection of these abnormalities by applying machine learning to thousands of healthy and diseased X-rays from over 15 countries, through which it has become accurate and reliable. The output of the CAD4TB® software is a score between 0 and 100, indicating the likelihood that the participant, above a threshold score, has possible, probable or definite (active) TB. The CAD4TB® software also outputs a 'heatmap' – a colour-coded image of the lungs indicating regions of abnormality.

#### 5.2 Summary of findings from clinical studies

AeoNose™: In recent years we performed several studies to test the AeoNose™ as a POC screening test, as well as a biomarker of treatment response. In a pilot study in 194 subjects in Bangladesh, a sensitivity of 93.5% and a specificity of 85.3% was detected discriminating healthy controls from TB patients. (Bruins, Tuberculosis 2013) In a pilot study in 110 subjects in Asuncion, Paraguay, the AeoNose™ showed a sensitivity of 88% and a specificity of 92%. (Coronel Teixeira, J Inf 2017) The device showed ease of operation and no adverse effects were observed. A field study in 2016 in an indigenous community in Paraguay (Puerto Casado) showed a specificity of 92% (IndiPaNose study, manuscript under revision), with no sensitivity calculated because of no actual active TB cases in the community. A pilot study assessing changes after initiation of therapy showed a fall in AeoNose™ signal correlating with treatment outcome (clinical signs and symptoms, CXR and sputum smear), demonstrating its potential as a biomarker for treatment response. (Elnosur study, poster presentation ERS congress 2015). An AeoNose™ study in 327 Indonesian patients differentiating pulmonary TB from suspected pulmonary TB demonstrated a lower sensitivity and specificity of 78-85% and 42-55%, respectively. The study indicated

the need for a large calibration group for better pattern recognition. The authors concluded that the AeoNose™ is better suited for screening purposes than clinical diagnosis. (Saktiawati, PLOS One 2019). The utility of the AeoNose™ for screening purposes was recently confirmed by researchers from Peru who demonstrated the possibility of using the AeoNose™ to identify high-risk patient who should receive confirmatory TB testing as part of a FAST strategy (Find cases Actively, Separate safely, and Treat effectively). AeoNose™ demonstrated a sensitivity of 85-93% and specificity of 63-73% in a population of 629 patients that underwent AeoNose™ analysis on admission to the hospital. (Nathavitharana et al., accepted abstract, The Union conference 2019)

CAD4TB®: CAD4TB® has been widely adopted over the past years, currently analyzing over 5000 CXR every day in clinics all over the world, including in prison facilities. The CAD4TB® software is going through continuous improvements. In a systematic review of CAD for detection of tuberculosis, version 1 and 3 of the software achieved AUC of 0.71-0.87 for sputum confirmed cases. (Pande, Int J TB Lung Dis. 2016) Version 5 of the software demonstrated an AUC of 0.90 in 47510 images with the clinical decision to treat as reference. (Melendez, Int J TB Lung Dis. 2018) Sensitivity and specificity is dependent on the selected threshold score. Threshold scores achieving high sensitivity (≥95%) can be reached with moderate-to-high specificity, performing similarly to expert radiologists. Version 6 of CAD4TB® was released in 2018. In a validation data set of 5665 CXR images the software attained an AUC of 0.987 for radiological reference and 0.885 for bacteriological reference (Murphy et al. Arxiv pre-print March 2019). CAD4TB® has already been tested as a triage tool to select presumptive TB cases for GeneXpert® testing. In a study in 388 South African presumptive TB cases, pre-screening with CAD4TB® version 3 led to an almost 50% reduction in cost per screened subject and cost per notified TB case, and more than doubled the number of subjects screened per day, at the expense of only a small number of missed cases. (Philipsen, Sci Rep 2015) These benefits were realized by guickly identifying TB negative subjects and reducing the total number of expensive and time-consuming NAAT tests.

## 6. METHODS

## 6.1 Study parameters/endpoint

6.1.1 Case definitions: Presumptive TB: Any participant with symptoms or signs suggestive of TB as judged by the study doctor.

## AND / OR

Any participant with CAD4TB output score above the threshold level (to be determined), or presenting with CXR abnormalities as judged compatible with TB by the study doctor.

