strains identified with Whole Genome Sequencing. Nature and extent of the burden and risks associated with participation, benefit and group relatedness:

Individual burden: all participants will perform one visit with a medical doctor for medical history, physical exam, digital X-ray (with CAD4TB®) and AeoNose sampling. Participants will be offered voluntary HIV testing and counseling. In case of presumptive TB (estimated 20-30% of participants) two sputum samples will be taken, either spontaneous or saline-induced. One sample is tested with GeneXpert and the other with liquid mycobacterial culture. Cases of presumptive TB with both negative GeneXpert® and culture results will be followed-up after three and six months for repeat testing.

Individual and group health benefit: all participants will have a medical consultation and CXR. In case of an alternative diagnosis, the prison health service will be notified. People diagnosed in the study with active TB will be notified and referred to receive treatment through the PNCT according to national guidelines. All participants will eventually benefit from less exposure to infectious TB cases through optimized infection control measures and treatment of infected individuals. The study will provide the PNCT with epidemiological data of this vulnerable group to optimize future TB control strategies.

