The digital CXR image will be analysed by CAD4TB® and the doctor will interprete the CAD4TB® output score and check the CXR for alternative diagnosis. All the findings by the study doctor will be recorded in the digital case record form. At the end of this visit the doctor will decide on health status of the participant: either the participant is considered healthy or a presumptive TB case.

For healthy participants the study ends after this 5th station.

- 6. Presumptive TB cases (see 6.1.1 Case definitions) will be asked to produce two sputum samples outside, preferably in the open air. Sputum can be either be produced spontaneously or via sputum induction with nebulized saline. Saline solution will be nebulized using a portable nebulizer. Sputum samples can deposited in standard containers. Samples will be stored in a cool box and transported to the laboratory the same day. Samples will then be processed and analysed by the National Reference Laboratory, Laboratory San Alfonso and IICS using GeneXpert® molecular testing and MGIT mycobacterial culture.
- 7. All participants will be educated about the importance of seeking medical care if symptoms compatible with TB emerge at any time.
- 8. In case a participant is passively identified with TB during the study period by the prison health services or PNCT, the study researchers will be notified. Clinical and microbiological data will be shared based on informed consent given by the participant.

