#### Follow-up of presumptive TB cases

Participants who are considered presumptive cases of TB at Visit 1, but with negative sputum results or unable to produce sputum, will be followed-up after three and six months.

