#### 8.1 Primary study parameter(s)

Primary study parameters are the number of TB cases cases by CAD4TB® CXR analysis and AeoNose™ breath sampling.

A binary assessment of the presence or absence of illness has four possible outcomes: true positives (TP), false positives (FP), true negatives (TN) and false negatives (FN). The relationship of the four outcomes is the basis of sensitivity and specificity analysis which determines the accuracy and predictive value of a diagnostic tool.

*True positive:* A positive test result in a confirmed TB case.

*False positive*: A positive test result with negative sputum results and no confirmed TB during follow-up.

*True negative*: A negative test result with no confirmed TB during follow-up. *False negative*: A negative test result with confirmed TB during follow-up.

Receiver operating characteristics (ROC) will be generated using an ROC package, and bootstrapping to generate confidence intervals in the ROC plot. T-testing or McNemar's test will be used to compute P values when comparing the sensitivity of conventional screening and CAD4TB® and AeoNose™ at assumed levels of specificity. We will also use multivariate analysis to analyse influences of different combinations of participant characteristics.

CAD4TB®: The collection of digital CXR images will be analysed and compared to presumptive and confirmed cases. The number of true/false positives and negatives will be used to calculate sensitivity and specificity as described above. The predictive value of the test will be analysed.

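### Untested index-negatives count as true negatives, and untested AeoNose-positives fit no cell, so section 8.1 overstates CAD4TB and conventional sensitivity and NPV if cases escape and leaves AeoNose specificity undefined

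*Protocol*

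**What the plan says.** **Who is tested.** Protocol section 6.1.1 gives three triggers for presumptive TB: symptoms or signs, the CAD4TB score ("Any participant with CAD4TB output score above the threshold level (to be determined"), or a film that the doctor judges compatible with TB. The Summary states: "In case of presumptive TB (estimated 20-30% of participants) two sputum samples will be taken". For everyone else, section 3 (Visit 1) says: "For healthy participants the study ends after this" fifth station. The visits at three and six months are for "Participants who are considered presumptive cases of TB at Visit 1, but with negative sputum results or unable to produce sputum".

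**What remains for the others.** Section 3 (Visit 1, steps 7 and 8) offers advice to seek care, and TB found by the prison health service or the national programme is reported to the study. Section 9.3 adds that trained health promotors already look for cases.

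**How results are classified.** Section 8.1 defines:
- true negative: "A negative test result with no confirmed TB during follow-up";
- false positive: "A positive test result with negative sputum results and no confirmed TB during follow-up";
- false negative: "A negative test result with confirmed TB during follow-up".

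Sensitivity, specificity and predictive value are calculated from these cells. The section names no rule or limitation for participants without a reference result.

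**The concern.** CAD4TB and conventional symptom screening are both index tests and routes to the reference standard. A TB case that is negative on both, and whose film the doctor also passes, gives no sputum and has no scheduled follow-up. Unless it is passively notified, section 8.1 moves it from false negative to true negative for both tests. Absolute sensitivity and NPV rise, and the report would present them as values for the whole prison population.

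The cells also do not match each other. A false positive requires negative sputum; a true negative does not. AeoNose triggers no testing, so many AeoNose-positive people will be unflagged and without sputum. Those without TB are neither false positives nor anything else in section 8.1, although AeoNose specificity belongs to the first primary objective. The false-negative cell, read literally, also leaves out index-negative cases confirmed at Visit 1.

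**Working it through.** **Inputs from the protocol.** 5000 invited and TB in 3-5% (section 3); 20-30% presumptive (Summary); CAD4TB sensitivity 95% and specificity 70% at a chosen threshold (section 1); AeoNose specificities between 63% and 92% from the screening-type studies and pilots in section 5.2.

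**Assumptions.** Conventional sensitivity 40-80% (not in the protocol); the doctor's film reading finds nothing beyond CAD4TB; no recovery by passive notification.

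**1. The plan's own figure.** 5000 × 0.03 = 150 and 5000 × 0.05 = 250, which reproduces the 150-250 cases of section 3. The steps below use 200 true cases (4%) and 4800 people without TB.

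**2. Number untested.** 5000 × 0.70 = 3500 to 5000 × 0.80 = 4000. At 95%/70%, CAD4TB alone would flag 0.95 × 200 + 0.30 × 4800 = 190 + 1440 = 1630 (32.6%), leaving at most 3370 untested.

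**3. CAD4TB and conventional screening.** Let m be the share of cases that escape everything. With independent triggers, m = (1 − CAD4TB sensitivity) × (1 − conventional sensitivity). Apparent sensitivity = true sensitivity / (1 − m). With 3360 true negatives among 3370 CAD4TB-negatives, true NPV = 3360/3370 = 99.70% and apparent NPV = (3360 + 200m)/3370.

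| Conventional, true | m | Cases escaping | CAD4TB apparent (true 95%) | Conventional apparent | NPV apparent |
|---|---|---|---|---|---|
| 80% | 1% | 2 | 96.0% | 80.8% | 99.76% |
| 60% | 2% | 4 | 96.9% | 61.2% | 99.82% |
| 40% | 3% | 6 | 97.9% | 41.2% | 99.88% |
| 60%, every CAD4TB miss escapes | 5% | 10 | 100% | 63.2% | 100% |

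The last row is the ceiling. Every escaped case is CAD4TB-negative, so at a true 95% no more than 5% can escape. If true CAD4TB sensitivity is instead assumed to be 80%, independent triggers give m = 4-12% and an apparent 83.3-90.9%.

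**4. What hardly moves.**
- Ratio of conventional to CAD4TB sensitivity: both are divided by the same (1 − m), so 0.60/0.95 = 0.632 before and after.
- McNemar test of these two at the operating threshold: escaped cases are negative on both and add no discordant pair.
- CAD4TB specificity: 3360/4800 = 70.0% against at most 3370/4810 = 70.1%.
- Case-count endpoints (section 6.1.2): they count cases found.

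**5. AeoNose specificity if people who fit no cell are left out.** Assume that specificity s is equal in flagged and unflagged people, that all 200 cases are flagged, and that all flagged people give sputum. Flagged people without TB number 1000 − 200 = 800 to 1500 − 200 = 1300. Only their false positives meet the definition, while all true negatives are kept: apparent specificity = 4800s / [4800s + (1 − s) × (800 to 1300)].
- s = 63%: 3024/(3024 + 481) = 86.3% to 3024/(3024 + 296) = 91.1%.
- s = 92%: 4416/(4416 + 104) = 97.7% to 4416/(4416 + 64) = 98.6%.

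The people affected number (1 − s) × (3500 to 4000), from 0.08 × 3500 = 280 to 0.37 × 4000 = 1480, before the calibration set is removed.

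**6. AeoNose sensitivity.** If AeoNose detects a fraction a of escaped cases and S of found cases, its true sensitivity is above or below the reported one according to whether a exceeds S. The protocol gives no information on a, so the direction is unknown.

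**7. Lower CAD4TB thresholds.** People scoring below the operating threshold are verified only if another trigger fires. That part of the ROC curve in section 8.1 therefore has no whole-population reference result.

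**The case against.** Triage before sputum is a normal design for mass screening. The main contrast between CAD4TB and conventional screening survives it, and section 2 states sensitivity and specificity as an objective for AeoNose only; for CAD4TB it speaks of feasibility and utility. A bias of 1-3 points is no larger than the sampling error: the 95% Wilson interval for 190/200 is about 91.0-97.3%. Passive notification and the health promotors will recover some cases, and a bounding analysis often sits in an SAP.

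Most of this stands and limits the point. It does not remove it. Section 8.1 does calculate CAD4TB sensitivity and predictive value. The bias has a known direction and does not shrink with sample size. Recovery is not systematic. The faulty cell rules stand in the protocol itself.

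Four stronger readings are tempting, and the documents do not support them.
- **That the plan drops untested AeoNose-positives.** Section 8.1 validates the model on all remaining participants and names no exclusion. This is a wording gap, and step 5 shows what would follow if it were filled by omission.
- **That CAD4TB sensitivity could be overstated by far more at the cited operating point.** Undetected TB in 0.5% of 3370-4000 untested people would be 17-20 cases, but only 10 of 200 can be CAD4TB-negative at a true 95%. A larger bias requires assuming a lower CAD4TB sensitivity.
- **That AeoNose sensitivity is shifted by a known amount.** Not even the sign is known.
- **That section 9.3 promises a reference test for everyone.** Its remark on investigating the entire group concerns who is enrolled.

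**Conclusion.** The point holds in limited form and should be fixed. Absolute CAD4TB and conventional sensitivity and NPV are overstated if a case escapes all three triggers and passive notification; if none escapes, there is no bias. At a true CAD4TB sensitivity of 95% the excess is about 1-3 points with independent triggers, and at most 5 points. Independence is itself uncertain, because the doctor sees the score and reads the same film. The escape rate, the conventional sensitivity and the recovery by passive notification are not in the protocol, so these are illustrations and not estimates.

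The gap in the AeoNose cells does not depend on escaped cases. It concerns roughly 280 to 1480 people under the stated assumptions, and leaving them out would inflate specificity from 63% to about 86-91%, or from 92% to about 98-99%.

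**What to change.** All changes are to section 8.1.

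1. Apply one rule to untested index-positives and index-negatives, for example no confirmed TB at Visit 1, at follow-up or by passive notification. Let confirmed TB in the false-negative cell include Visit 1.
2. State that sensitivity and NPV are relative to cases found by the combined trigger plus passive notification.
3. Add a bounding analysis over a stated range of undetected TB in the untested. Keep the range consistent with the assumed CAD4TB sensitivity, and use only the validation set for AeoNose. The numerical range may sit in the SAP.
4. Make no whole-population accuracy claim for CAD4TB thresholds below the operating one.

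The cost is a few sentences and one analysis, with no extra sputum, visits or participants. The downside is a narrower claim and a less favourable range. Passive notification is incomplete, so it can inform the bound but cannot close it.
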